### **Mindfulness and Acceptance**

The two measures of mindfulness and distress tolerance include: (1) The 10-item Child and Adolescent Mindfulness Measure (CAMM; Greco et al., 2011), which has adequate reliability and is predictive of favorable outcomes (e.g., grades). Co-I [name] recently evaluated the CAMM with a sample of 19-32 year old adults with ASD. Cognitive interviews and reliability analyses indicated that the CAMM was well understood and demonstrates acceptable internal consistency ( $\alpha = .831$ ) and excellent test-retest reliability ( $ICC_2 = .956$ ) with an adult ASD sample ([name], 2017); (2) The Brief Experiential Avoidance Questionnaire (BEAQ; Gamez et al., 2014) is a 15-item version of the 62-item Multidimensional Experiential Avoidance Questionnaire (MEAQ; Gamez et al., 2011). The BEAQ has good internal consistency and strong convergence with the MEAQ.

### **Treatment and Assessment Fidelity**

Participants will complete a Treatment Satisfaction Scale to obtain their impressions of the overall impact of the interventions. After each session, the clinician will complete a Fidelity Rating form that assesses client homework completion, session rapport, client involvement, and adherence to the manual. There are separate fidelity forms for EASE and ACC, with the checklist for EASE emphasizing key ingredients to cover, and the ACC checklist confirming that prohibited strategies were not introduced. At least 20% of the sessions will be observed and independently coded by two raters to ensure fidelity agreement. Finally, the Site PIs will watch occasional sessions in entirety for fidelity to prevent drift, and for supervision purposes.

### **Parent Self-Report Measures.**

Given variability in parental functioning and the potential for parental influences on outcome, we will obtain brief parental ratings. We will repeat these at post-treatment, to enable future explorations of any potential benefits experienced by the parents themselves. Measures will include the: (1) Parenting Stress Index, Fourth Edition- Short Form (PSI-4; Abidin, 2012), a 36 item self-report questionnaire of parenting stress that contains Parental Distress, Parent-Child Dysfunctional Interaction, and Difficult Child subscales; the PSI has been utilized extensively in ASD research, including above the traditional age cutoff of 12 years (Pedersen et al., 2016; Simonoff et al., 2012); (2) The State-Trait Anxiety Inventory (STAI; Spielberger et al., 1983), a 40-item self-report questionnaire that assesses trait and state, or current, anxiety symptoms; and (3) the BEAQ, as described above.

**Table 2.** Schedule of Measure Administration

| Measure  | Each Visit  | Eligibility   | Pre-Trmt   | Midpoint   | Post-Trmt  | Follow-up  |
|--|---|---|--|--|--|--|
| CHARACTERIZATION                          |   |   |  |  |  |  |
| Demographics                                     |   |  |  |  |  |  |
| Autism Diag. Obs. Schedule-2                     |   |  |  |  |  |  |
| Wechsler Abbrev. Scale of Intell-2               |   |  |  |  |  |  |
| Delis-Kaplan Executive Functioning System        |   |  |  |  |  |  |
| Intolerance of Uncertainty Scale                 |   |   |   |  |   |  |
| Social Responsiveness Scale-2                    |   |   |   |  |  |  |
| Pubertal Development Scale                       |   |   |   |  |  |  |
| Needs assessment                                 |   |   |    |  |  |  |
| Medications/Treatments                           |   |  |   |    |   |   |
| EMOTION REGULATION                        |   |   |  |  |  |  |
| Emotion Dysregulation Inventory                  |    |  |    |    |       |       |
| Response to Social Stress Quest.                 |   |   |    |       |    |    |
| FUNCTIONAL/ADAPTIVE OUTCOME MEASURES      |   |   |  |  |  |  |
| Clinical Global Impressions                      |   |   |   |  |   |   |
| Child & Adolescent Functional Assessment         |   |   |   |  |   |   |
| PSYCHIATRIC SYMPTOMS AND PROBLEM BEHAVIOR |   |   |  |  |  |  |
| Brief Psychiatric Rating Scale                   |   |   |   |  |   |   |
| Achenbach System:
CBCL/YSR; ABCL/ASR; TRF     |   |   |    |     |    |    |
| Aberrant Behavior Checklist                      |   |   |    |    |    |    |
| PROMIS Anxiety                                   |   |   |    |   |    |    |
| PROMIS Depression                                |   |   |    |   |    |    |
| MINDFULNESS / ACCEPTANCE                  |   |   |  |  |  |  |
| Brief Experiential Avoidance Questionnaire       |   |   |   |    |   |   |
| Child & Adol. Mindfulness Measure                |   |   |   |    |   |   |
| FEASIBILITY                               |   |   |  |  |  |  |
| Treatment Satisfaction                           |   |   |  |  |    |  |
| Treatment Fidelity                               |  |   |  |  |  |  |
| PARENT SELF-REPORT MEASURES               |   |   |  |  |  |  |
| Parenting Stress Index SF                        |   |   |   |  |   |  |
| Brief Experiential Avoidance Questionnaire       |   |   |   |  |   |  |
| State Trait Anxiety Inventory                    |   |   |   |  |   |  |

-  Clinician with participant (e.g., performance based, interview, or direct observation)
-  Parent-report
-  Self-report
-  Other-report
-  Assignment naïve rater
-  Clinician rating

## 1.J.a. STATISTICAL PLAN AND DATA ANALYSIS

### **Justification of sample size that is necessary to achieve the desired power**

We will enroll 80 subjects at two sites. Using small-scale pilot pre-post repeated measures data ( $n = 12$ ), we estimated the sample size to achieve the power of 0.80 for testing each hypothesis stated in the Aims 1 and 2 above from the EASE open trial. For the hypotheses to provide evidence that EASE has a differential treatment effect on ER, functional impairment, psychiatric symptoms, and problem behaviors (hypotheses 1a, 1b, 2a, 2b), Cohen's  $d$ , or standardized mean difference, ranged from small-to-medium effect size (0.41 for Anxiety) to very large (2.81 for CGI-I). The necessary sample size to detect the smallest effect size was computed as a total of 49 (per group), with a range of 4 to 28 per group for all other outcomes with larger effect sizes, and an average across measures of 17 per group. Our primary interest is in effects with at least moderate effect sizes, as they are likely to have the most real-world impact. As such, even if there was significant attrition, we should have ample power to detect the most meaningful outcomes for Aim 1 and Aim 2. To test the mediation effects (Exploratory Aim 4), we obtained the required sample size using the methodology proposed by Judd et al. (2001) and elaborated by Montoya & Hayes (2017). A necessary condition to detect mediation is that the change score for a mediator needs to be statistically significantly associated with the change score in dependent variable after controlling for the average level of the mediator. Using this framework, we found that the necessary total sample size to detect the mediation effect with power of .80 ranged from 43 to 86 (per group), where the effect size as a partial correlation in multiple linear regression ranged from large (0.44, path: Treatment  $\rightarrow$  CAMM Mindfulness  $\rightarrow$  RSQ Involuntary Disengagement) to medium (0.31, path: Treatment  $\rightarrow$  EDI reactivity  $\rightarrow$  Depression). The maximum sample size that we can feasibility ascertain for this project is 80, which gives us a chance to detect mediation processes that have large effects; accordingly, this aim is considered exploratory.

**General analytic approach.** Data will be analyzed based on CONSORT recommendations using intent-to-treat analyses with all participants who receive any exposure to their respective treatment condition. General linear models (analysis of variance [ANOVA] mixed models) will evaluate the differential trajectories of change between participants treated with EASE and ACC, after adjusting for demographic, medication, and other treatment confounders. It is *hypothesized* that participants who receive EASE will demonstrate significant differential improvements in ER, psychiatric symptoms, problem behavior, and functional impairments compared to the ACC. In addition, it is *hypothesized* that participants who receive EASE will maintain their gains at 3 months post-treatment compared to those treated with ACC. Exploratory analyses will also examine whether ER and mindfulness serve as mechanisms of change using a mediator analytic framework.

Because our population of interest is, by definition, vulnerable and their symptoms rapidly fluctuating, we believe it is insufficient to employ a traditional pre-post design for determination of treatment impact. For instance, a client might be responding well to treatment but then face the start of the school year immediately before the last session and experience heightened dysregulation; an analytic design that does not consider this will yield results that do not fully capture the pattern of growth. As such, we have refined our data collection procedures to include assessment of ER data at every session, which allows us to track our theorized mechanism of change in a nuanced way. We have also considered this issue in our analytic plan. After first utilizing traditional mixed model group comparisons of change, a more sophisticated analysis will be conducted using hierarchical linear models (HLM), which is also known as multilevel growth modeling (Raudenbush & Bryk, 2002). HLM casts the changes as the growth trajectories over time and allows us to examine the average amount of change, the amount of individual differences, and the correlates of changes between groups.

**Medication effects.** While randomization procedures should ensure comparable medication usage between treatment groups, given the modest sample size, differences in medication usage will be explicitly examined between treatment groups, and statistically controlled for in efficacy analyses if necessary.

**Intent to Treat Analyses and Approach to Missing Data.** Automated systems are in place via our online data collection (piloted during our open trial) to minimize occurrence of missing data. Nonetheless, intent-to-treat analyses of treatment effects will include all 80 individuals, regardless of attrition or infidelity to treatments. Both of our analytic approaches allow for missing data. ANOVA mixed models do not require that subjects be

excluded from the analyses because of a single missing data point. Multilevel growth models can also make an efficient estimation by utilizing all the available data, and further, the estimates are valid (i.e., asymptotically unbiased) when missingness occurs at random (MAR) (Little & Schenker, 1995). Even when MAR is not satisfied, the robustness of the results is maximized when all available data are used in the analysis (Schafer, 1997). In order to accommodate the case of missing ‘not at random,’ we plan to conduct a sensitivity analysis to see how much our inferences would be altered using a pattern-mixture model (Hedeker & Gibbons, 2006).

**Controlling Experimental-Wise Type I Error Rates.** The conduct of multiple tests of statistical inference can artificially increase Type I error rates. Several approaches will be used to control the experimental-wise error rate in this trial. First, analyses conducted to test the hypotheses of Aims 1 through 3 will be given priority over exploratory analyses conducted as part of Aim 4. Since these hypotheses about efficacy and durability of the proposed EASE program on ER and functional impairment have confirmatory nature from our prior studies and are the main hypotheses in this clinical trial, we will employ Hochberg’s correction (Hochberg, 1988) to control the experimental-wise error rate by adjusting p-values for multiple hypothesis tests in order to rigorously examine the treatment efficacy and durability. Second, in order to address the hypotheses in Aim 4, outcome measures will initially be aggregated into four multivariate composite domains (i.e., ER, functional impairment, psychiatric symptoms, and problem behaviors) based on internal consistency analyses and previous studies, which will reduce the number of hypothesis tests initially conducted. Then, exploratory analyses will be conducted for individual measures within these composite domains only if the overall multivariate composite demonstrates a significant mediation effect.

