**1.I.b. Control Intervention – Supportive Therapy**

Although we considered an inactive control condition, such as a wait-list group, we opted for a more scientifically rigorous design for 3 reasons. First, use of an active control condition (ACC), will allow us to test the efficacy of the ‘active’ ingredients of EASE (i.e., mindfulness, emotion awareness, ER strategies). Second, with the inactive control, we would not be able to rule out the effect of factors such as the therapeutic relationship and familial expectation of treatment benefit. Third, use of the active comparator allows for a more rigorous test of effect via independent, assignment-naïve (‘blinded’) evaluators. The ACC will involve non-directive, supportive psychotherapy and education, which is a well-established ACC, often used in RCTs involving youth (e.g., Piacentini et al., 2010) and in trials evaluating MBIs (e.g., Shallcross et al., 2015). We structured the ACC based on guidelines set forth by clinical trial methodologists (e.g., Baskin et al., 2003; Kazdin et al., 1990). The ACC is *structurally equivalent* to the experimental intervention in that it is implemented by the same therapists, over 16 50- to 60- minute sessions, in an individual format. Additionally, the purported *active ingredients* of EASE are expressly contraindicated in the ACC. In the ACC, the clients and parents will be allowed to discuss any topics and stressors with the therapist, but the therapist is prohibited from providing mindfulness training.

**1.I.c. Overview.** We propose to conduct a sufficiently powered RCT of EASE, across two clinical sites. The design and participant flow is depicted in Figure 6.

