### **Statistical Analyses by Aim**

#### **Aim 1 (Primary Outcome): Show that EASE improves emotion regulation.**

First, to test the main effects of EASE on impaired ER (Hyp 1a) and maladaptive ER strategy use (Hyp 1b), we will employ linear mixed-effects models, with an auto-regressive error structure most appropriate to longitudinal data, allowing model intercepts and longitudinal trajectories to vary across subjects. Significant treatment by time interactions showing differences in linear rates of change in EDI Reactivity (Hyp 1a) and RSQ Involuntary and Voluntary Engagement scores (Hyp 1b) will be the effects of interest in these models. All mixed-effects models will control for potential demographic and medication confounds by including age, gender, IQ, and medication information as model covariates. This will be followed by modeling of growth trajectories between groups via HLM, also controlling for relevant potential confounds, using weekly data for Hyp 1a (EDI), and pre, mid, and post-treatment data for Hyp 1b (RSQ).

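### The per-group sample sizes are single-group pre-post sizes, so 0.80 power for each EASE-versus-ACC hypothesis is not shown

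*Combined protocol and SAP*

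**What the plan says.** The sample-size paragraph of 1.J.a describes its source as "Using small-scale pilot pre-post repeated measures data" from 12 participants. Its stated purpose is that "we estimated the sample size to achieve the power of 0.80 for testing each hypothesis stated in the Aims 1 and 2". It takes Cohen's d from 0.41 (anxiety) to 2.81 (CGI-I) as the differential treatment effect for hypotheses 1a, 1b, 2a and 2b. It then reports: "The necessary sample size to detect the smallest effect size was computed as a total of 49 (per group". For the remaining outcomes it gives sizes between 4 and 28 in each group, and its mean over the measures is 17. Having limited its interest to effects of at least moderate size, it concludes that "even if there was significant attrition, we should have ample power to detect the most meaningful outcomes for Aim 1 and Aim 2".

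The analysis is a comparison between arms. Under Aim 1 the effects of interest are "Significant treatment by time interactions showing differences in linear rates of change in EDI Reactivity", and the same interaction for the RSQ. Section 1.I.d plans 80 enrolled and 60 after 25% attrition. Randomization is to equal numbers, so about 40 and 30 per arm. Section 1H calls the trial sufficiently powered, and 1.I.c repeats it: "We propose to conduct a sufficiently powered RCT of EASE, across two clinical sites".

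**The concern.** Section 1.F defines the pilot d as mean pre-to-post change divided by its SD, tested with a paired t-test in a single group. A between-arm comparison differs in two ways. The difference of two means has twice the sampling variance at the same n per group, so the required n per group roughly doubles. The effect is also EASE change minus ACC change, so the pilot d carries over only if ACC participants do not change at all.

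The plan gives reason to doubt the second condition. Section 1.I.b rejects a wait-list because with one "we would not be able to rule out the effect of factors such as the therapeutic relationship and familial expectation of treatment benefit". An active control was chosen because those factors may produce improvement, yet the sample-size text allows for none.

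If the stated sizes answer the single-group question, the quantitative basis for the power claim does not apply to this trial. A reader of a null result would be misled about what the trial could have detected.

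**Working it through.** **Inputs.** The d values in pilot Table 2 (section 1.F) are CGI-I 2.81, EDI Reactivity 0.73, RSQ involuntary engagement 2.67, depression 0.88, ABC-Irritability 0.79 and anxiety 0.41. They are within-person: anxiety is 4.46/10.85 = 0.41 and EDI is 0.49/0.67 = 0.73. Power is 0.80. Alpha is not stated for the sizing; two-sided 0.05 is assumed.

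**Step 1: reproduce the plan's figures.** For a one-group paired test, power is P(|T| > t_crit) for a noncentral t with n − 1 df and noncentrality d√n. For two groups of n, df is 2n − 2 and noncentrality is d√(n/2). The smallest n reaching 0.80 is:

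| Measure | d | One group, paired | Two arms, per group |
|---|---|---|---|
| CGI-I | 2.81 | 4 | 4 |
| EDI Reactivity | 0.73 | 17 | 31 |
| RSQ | 2.67 | 4 | 4 |
| Depression | 0.88 | 13 | 22 |
| ABC-Irritability | 0.79 | 15 | 27 |
| Anxiety | 0.41 | 49 | 95 |
| Mean | | 17.0 | 30.5 |

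The paired column gives the stated 49, minimum 4 and average 17. The 4 does not discriminate, since both columns give it; the 49 and the mean of 17.0 do. Read as a two-group size, 49 would need d = 0.57, which is not tabulated.

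The stated 28 does not reproduce. The next paired size below 49 is 17, and adding 28 to the six values gives (102 + 28)/7 = 18.6. A paired 28 needs an untabulated d of about 0.55, which is about 53 per group between arms.

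**Step 2: power of the stated size.** With 49 per group and d = 0.41, the two-arm noncentrality is 0.41 × √24.5 = 2.03 and power is 52%. Even at face value, 49 per group is 98 people, above the 80 planned.

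**Step 3: power at the planned size.** Two-sample t-test on change, unadjusted 0.05, taking the pilot d as the between-arm effect (no ACC change):

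| Effect | 40 per arm | 30 per arm |
|---|---|---|
| RSQ, 2.67 | >99% | >99% |
| Depression, 0.88 | 97% | 92% |
| ABC-Irritability, 0.79 | 94% | 85% |
| EDI, 0.73 | 90% | 79% |
| d = 0.5 (assumed for moderate) | 60% | 48% |
| Anxiety, 0.41 | 44% | 35% |

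The smallest d with 80% power is 0.63 at 40 per arm and 0.74 at 30 (0.70 and 0.81 at alpha 0.025, to illustrate a multiplicity cost).

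**Step 4: sensitivity to ACC change.** At 40 per arm, EDI keeps 0.80 only if ACC improves by at most 0.73 − 0.634 = 0.096 SD of change, which is 13% of the pilot gain. The documents give no ACC change, so the following is illustrative. If ACC achieves 25% of the EASE gain, d is 0.5475 and power is 68% / 55% at 40 / 30 per arm. At 50%, d is 0.365 and power is 36% / 28%. The pilot d is itself imprecise: for 0.73 with n = 11, the 95% interval is about 0.05 to 1.39.

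**Step 5: CGI-I.** The 2.81 is mean change from a score of 4, but Aim 2 analyses responders (scores 1 or 2) against the rest. With n = 12, mean 2.25 and every score between 1 and 3, only one count matches the Table 2 SD of 0.62: one 1, seven 2s and four 3s, so 8/12 = 67% responders. Normal-approximation power at 40 / 30 per arm is 99% / 97% against an assumed control rate of 20%, 92% / 83% against 30%, and 67% / 55% against 40%.

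**The case against.** **Another route also gives 49.** A two-group repeated-measures interaction with f = d/2 and an assumed correlation of 0.5 gives 5, 17, 5, 13, 15 and 49, mean 17.3. Those are total sizes, so 49 would be about 25 per group. The minimum is 5 rather than the stated 4, and the implied difference in change is 2 × 0.41 = 0.82 SD. The origin of the figures is therefore not certain, and the 28 fits neither route. Neither route supports 49 per group at d = 0.41.

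**The plan does not say that 80 delivers 0.80 for every outcome.** Its own 49 exceeds 40 per arm, and it restricts interest to at least moderate effects. That is a fair reading of the anxiety shortfall. It does not rescue the conclusion for moderate effects if moderate means about 0.5; the plan gives no value, and all its other pilot effects are 0.73 or larger.

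**The t-test is conservative.** The mixed model uses all 80 participants and repeated measures, weekly for EDI. This stands, but the plan quantifies no gain. Hochberg's correction works the other way. Because it is a step-up procedure, its cost may be small when a companion test is very highly powered, so the 0.025 figures illustrate a bound for two tests. The plan's family spans Aims 1 to 3, and the net effect is not known.

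**EDI at 30 per arm is borderline.** The section 1.F text gives 0.74 and Table 2 gives 0.73; power is 80.5% or 79.4%. The text's p = .06 does not match the Table 2 row (p = .037), and the choice changes nothing of substance.

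**Conclusion.** The concern holds. The stated 49, 4 and 17 are the sizes for single-group pre-post tests, and no two-group calculation tried gives 49 per group at d = 0.41. The corresponding two-arm requirement is 95 per group for anxiety and 31, not 17, for the primary EDI measure, and both assume that ACC has no effect.

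This does not show that the trial lacks power. With no ACC change, the RSQ, depression and ABC-Irritability effects exceed 0.80 at either size, and EDI has 90% / 79%. What is not shown is 0.80 for each hypothesis, or ample power for moderate between-arm effects after attrition. On this calculation, the EDI figure rests on an unstated assumption of almost no ACC improvement. CAFAS and BPRS, both named for Aim 2, have no effect in pilot Table 2, so they have no stated basis at all.

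The figures assume two-sided 0.05 without multiplicity adjustment, equal arms, and a t-test on change in place of the mixed model.

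**What to change.** Keep N = 80 and restate the sample-size section of 1.J.a:

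1. Replace 49, 4 to 28 and the average of 17 with two-group sizes (anxiety 95, EDI 31, ABC-Irritability 27, depression 22, RSQ 4). State the alpha and sidedness. Identify the measure behind 28 or remove it.
2. State beside those sizes that the pilot d values are uncontrolled and imprecise, and equal the between-arm effect only if ACC produces no change. Label any scenario with ACC improvement as illustrative.
3. Here and in 1H and 1.I.c, replace the ample-power and sufficiently-powered wording with the minimum detectable between-arm difference: 0.63 SD of change at 40 per arm and 0.74 at 30, at unadjusted 0.05. Note that it may be larger under Hochberg, and that the t-test is a conservative proxy for the mixed model on all 80.
4. Give CGI-I power as a comparison of responder proportions, with the control rate stated as an assumption and a range shown, for example 20% to 40%.
5. It would also help to say that CAFAS and BPRS have no pilot effect estimate.

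The cost is the rewording of one section and two phrases elsewhere, and a less favourable stated power. No participants, assessments or analyses change.

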## 1H. AIMS

**The primary objective of this study is to formally evaluate efficacy of EASE via a sufficiently powered, two-site randomized-controlled trial (RCT).** Our aims are consistent with several FY17 ARP **areas of interest**; specifically, EASE: (1) is a behavioral, non-pharmacological therapy that (2) alleviates co-occurring conditions (e.g., depression, aggression, anxiety), and (3) promotes success during the transition to adulthood. This proposal is innovative in many aspects, perhaps most substantially in that it targets a theoretically and empirically based transdiagnostic process (i.e., impaired ER) during a critical transitional period during development. As such, and consistent with the spirit of the ARP Clinical Trial Award, this research is expected to have a major impact on the treatment of ASD.

A total of **80 adolescents and young adults with ASD** (age 14-21, inclusive) will be randomly assigned to either EASE or an active control condition (ACC), consisting of supportive therapy that is matched on therapist time to EASE but does not contain EASE's active ingredients (e.g., mindfulness).

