Randomization. Participants will be randomly assigned to EASE or ACC once eligibility is confirmed, by a data manager independent from the PIs and clinical team. Randomization algorithms have been created by the study statistician, independent of the PIs. Randomization will be done to ensure equal numbers of EASE and ACC at each site. Group assignment will be communicated to the PIs and assigned study clinician, who will then inform the participant. Site PI's ([name] and [name]) will closely monitor screening and randomization procedures and, should difficulties (e.g., more withdrawals from ACC than active) arise, they will be addressed immediately with the Data Safety and Monitoring Board.

Therapist training: At the start of the RCT, all therapists will convene for a training meeting for both treatments, on site at Pitt. The PIs will provide the theoretical background and didactic training, including live and video (from open pilot) demonstration of specific strategies. Study therapists must observe each recorded session (from open trial) before delivering that session with a study participant. In addition, every session of the first case of every therapist will be observed for integrity and training purposes by the respective site PI.

'Blind' maintenance: All Independent Evaluators will be 'blind,' or naive, to treatment assignment, and they will instruct participants not to reveal what intervention that they are receiving during the course of the procedures. Meetings with the independent raters will be conducted in a different office than the therapy, and the therapists and PI's will not be involved in outcome assessment. Regular assessments of treatment naive status will be conducted by the PI. When questions arise about possible need to break the blind (e.g., a potentially serious event becomes apparent during an assessment, but evaluator is not aware of treatment condition), [name] (Co-I at Pitt) will be the first contact. She will work with the PI's to determine how to proceed. If a participant breaks the blind, we will get another rater.

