## 1.1.e. Study Variables and Measurement

A multi-method, multi-informant assessment battery (see Table 2) will be used to provide accurate sample characterization and examine change. All measures have well-established psychometric properties for the full age range of our sample and have been used with ASD samples. We are employing **four primary reporters**: self, parent, other (e.g., teacher, co-worker), and assignment-blind clinical rater, and **four modalities of assessment**: direct testing, observational, questionnaire, and interview. Assessments will be completed at pre-treatment (baseline), midpoint (8 weeks), post-treatment (16 weeks), and follow-up (3 months after post-treatment), in addition to the primary measure of ER completed weekly by parents.

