### Primary Outcome (Emotion Regulation) Measures:

We have two measures of our primary outcome: (1) The EDI, which measures impaired ER, collected weekly parent report (short form), other reporter at pre-, post- and follow-up, and blind rater interview of the participant at pre-, post- and follow-up; and (2) The RSQ self- and parent report as a measure of ER strategies, collected at pre-, mid- and post-treatment, and 3-month follow-up.

Emotion Dysregulation Inventory (EDI; [name] et al., 2016). The EDI was developed to assess the full range of ER impairment observed in ASD. The item pool was created with feedback from parents of youth and young adults with ASD and input from a panel of experts in measure development and ER in ASD. Next, caregivers of 1,755 youth with ASD completed 66 candidate EDI items, and the final 30 were selected based on factor analysis and item response theory (IRT) analyses. The EDI has two scales: 1) *Reactivity*, characterized by intense, rapidly escalating, sustained and poorly regulated negative emotional reactions, and 2) *Dysphoria*, characterized by minimal positive affect and motivation, and the presence of nervousness and sadness. A 7-item Reactivity short form was developed via simulated computerized adaptive testing, which is correlated .98 with the full scale. Validity evidence was supported by expected group differences (higher scores in an ASD

psychiatric inpatient versus community sample), expected correlations with measures of related constructs, and demonstration of change sensitivity. Co-calibration with legacy measures demonstrated that the EDI provides substantially more information on individual variability in ER; Figure 7 shows these test information curves for the full EDI Reactivity scale, the 7-item EDI short form, the ABC-I (15 items), an emotion dysregulation index from the CBCL (Sampson et al., 2014), and CBCL Stress Problems Scale. In a sample of 432 youth with ASD with stable treatments, paired samples t-tests across a 4-week period yielded a very small effect size (-0.06), which will be helpful in judging the meaning of EDI effect sizes for EASE.

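### The plan gives two different intent-to-treat sets, one limited to participants exposed to treatment and one covering all 80 randomised; the exposure condition should be deleted

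*Combined protocol and SAP*

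**What the plan says.** Two paragraphs of section 1.J.a define the analysis set.

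- *General analytic approach*: "intent-to-treat analyses with all participants who receive any exposure to their respective treatment condition". Exposure is not defined.
- *Intent to Treat Analyses and Approach to Missing Data*: "intent-to-treat analyses of treatment effects will include all 80 individuals, regardless of attrition or infidelity to treatments".

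Section 1H gives 80 as the number to be randomly assigned, so the second rule describes everyone randomised.

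The *Randomization* paragraph of section 1.I.d bears on who starts treatment. It says "Group assignment will be communicated to the PIs and assigned study clinician, who will then inform the participant". It also says that "should difficulties (e.g., more withdrawals from ACC than active) arise, they will be addressed immediately with the Data Safety and Monitoring Board".

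On data collection, section 1.1.e sets assessments by time: "midpoint (8 weeks), post-treatment (16 weeks), and follow-up (3 months after post-treatment), in addition to the primary measure of ER completed weekly by parents". The primary outcome section likewise describes the parent-report EDI as weekly. *General analytic approach* describes the same stream by attendance: "we have refined our data collection procedures to include assessment of ER data at every session".

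**The concern.** Someone who attends one session and then leaves is in both sets. Someone who is randomised and never attends is in the second set only. Such a person already knows the assigned arm, so the decision not to start can depend on it. Dropping these people after randomisation produces a modified set under an intent-to-treat label and removes the protection that randomisation gives to the comparison.

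An analyst could follow either paragraph and truthfully report that the plan was followed. The choice of set should not be open once arm membership and attendance are known.

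A second gap follows. Under the all-randomised rule, people who never start inform the treatment-by-time effect mainly if their later assessments are obtained. The plan does not say whether someone who attends no session is still assessed.

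**Working it through.** **1. Counts.** Sites (section 1.I.d): 50 + 30 = 80. The plan's allowance for attrition reproduces: 80 × (1 − 0.25) = 60. Allocation is equal, so 40 per arm. The all-randomised set is 80. The exposed-only set is 80 minus the number who never start. The plan gives no rate for this; an assumed 0, 2.5, 5 or 10% gives 80, 78, 76 or 72.

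**2. Set-up for scale.** The Aim 1 model has random intercepts and slopes with autoregressive errors. Take outcome = intercept + arm + time + arm × time, with time 0 at pre-treatment and 1 at post-treatment, no true effect, and k people in one arm who never start. All variances are assumed, in units where baseline variance is 1:

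- intercept variance 0.5, 0.6 or 0.7, with residual variance 0.5, 0.4 or 0.3
- slope variance 0.3 or 0.4
- intercept-slope covariance −0.2, −0.1 or 0
- error correlation 0.3 between adjacent measurements.

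**3. Case (a): only baseline data from those who never start**, who are d0 = 0.5 or 1.0 SD worse at baseline. In the affected arm, the change from including them is the slope element of

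[(40 − k)A + kE]⁻¹ (k·d0, 0)′,

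where A = X′V⁻¹X is the information from one person with complete data and E has 1 in the intercept cell and 0 elsewhere.

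Worked example: three waves, intercept variance 0.5, slope variance 0.3, covariance −0.2, k = 6, d0 = 1.

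- A has entries 1.630 (intercept), 0.882 (cross) and 1.304 (slope).
- 34A + 6E has entries 61.40, 29.99 and 44.33.
- Determinant = 61.40 × 44.33 − 29.99² ≈ 1822.8.
- Slope shift = −29.99 × 6 / 1822.8 = −0.099 SD.
- SE = √(61.40/1822.8 + 1.630/(40 × 1.347)) = √(0.0337 + 0.0303) = 0.253, where 1.347 is the determinant of A.
- Ratio = 0.099/0.253 = 0.39.

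Over the whole grid:

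| Data | k | Shift (SD) | Largest shift/SE |
|---|---|---|---|
| Three waves | 2 | 0.007 to 0.033 | 0.13 |
| Three waves | 6 | 0.021 to 0.099 | 0.39 |
| Weekly, 17 points | 2 | 0.004 to 0.023 | 0.11 |
| Weekly, 17 points | 6 | 0.012 to 0.071 | 0.34 |

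These are not bounds. With intercept variance 0.4, the three-wave figure for k = 6 reaches 0.112 SD (0.42 SE).

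**4. Case (b): scheduled outcomes obtained**, with change in those who never start differing by 0.5 SD from change in those who do. Shift = (k/40) × 0.5, which is 0.025 SD for k = 2 and 0.075 SD for k = 6. With SE of about 0.21 to 0.26 (three waves) or 0.17 to 0.21 (weekly), this is 0.10 to 0.14 SE and 0.29 to 0.43 SE.

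**5. Power cost of the all-randomised rule.** Take the pilot EDI Reactivity d = 0.73 as if it were a between-arm effect (it is a pre-post figure, used here only for scale) and two-sided alpha 0.05 (assumed), with power = Φ(d√(n/2) − 1.96). If 10% never start and gain nothing, all 80 gives d = 0.73 × 0.9 = 0.657, n = 40 and power 0.836. The 72 exposed give d = 0.73, n = 36 and power 0.872.

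**The case against.** The paragraph devoted to intent-to-treat is unambiguous about including all 80, and on an ordinary reading it governs. The exposure phrase sits in an overview sentence that also invokes CONSORT, and it may have been meant inclusively, to keep partial attenders. That is a fair reading and limits the point to a minor one. It does not remove the conflict, because the overview is written as a general rule and nothing subordinates it.

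The reference to more withdrawals from the control arm is a conditional example of a reason to contact the monitoring board. It is not a prediction, and it concerns withdrawal rather than never starting. It shows only that arm-related departure was thought possible.

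For anyone attending as planned, weekly and every-session collection coincide, since both arms have 16 sessions and the programme runs over 16 weeks. The follow-up gap therefore concerns only people who do not attend as planned.

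The numerical illustration is nearly all assumption. In the pilot (section 1.F), 2 of 20 enrolled participants dropped out at any stage, so at most 10% never started, which would be 4 of 40. The pilot was small, had one arm and was still running, so it does not settle the control-arm rate, but six in one arm and none in the other is a harsh case. An adjacent-measurement correlation of 0.3 also cannot hold at both 8-week and 1-week spacing: 0.3 at 8 weeks implies 0.3^(1/8) = 0.86 weekly. With that value the weekly k = 6 range becomes 0.020 to 0.098 SD (up to 0.39 SE), so much of the apparent advantage of weekly data comes from the assumption. These criticisms stand, but they affect only the illustration.

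**Conclusion.** The concern holds and is minor. Two current paragraphs give incompatible definitions under one label, so the exposure rule is wrong as written and is more than a missing detail. The practical effect is unknown, zero if everyone starts and likely small. In the illustrations it stays below half a standard error even with six people who never start, all in one arm. Apart from 80 randomised in equal arms, every input to those shifts is assumed. Case (a) also assumes that the pre-treatment battery is complete for people who never start; the plan places randomisation at confirmed eligibility and does not say.

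The conflict between the definitions does not depend on these figures. The unstated follow-up of people who never start is a secondary point of clarity.

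**What to change.** 1. Delete the exposure condition under *General analytic approach*.
2. State once that the primary set is all randomised participants, analysed in the arm assigned, whether or not any session was attended. All randomised is safer than a fixed 80, since the number actually randomised may differ.
3. If an exposed-only analysis is wanted, define exposure and label it a sensitivity analysis.
4. Add one sentence saying that the fixed-time assessments and the weekly parent-report EDI are sought from those who never start or who withdraw, where they agree.

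The cost is one clause, one sentence, a little follow-up effort and slightly more missing data in the primary set. The mixed models and the planned pattern-mixture sensitivity analysis already address missing data. In the illustration above, the power difference is 0.872 − 0.836 = 0.036.
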